10.2 Secondary study parameter(s)

For the secondary analysis, the aforementioned GLMM analyses on number and type of complications and clinical visits will be repeated comparing the 3 groups, namely the RFU, active COD and passive COD.

Secondary patient-reported outcomes, namely PROMIS physical function, NPRS, NSRS and EQ-5D-5L, will be presented as mean with standard deviation in case of normality or median and interquartile range otherwise. These parameters will be analysed using linear mixed models, with repeated measures clustered within participants and participants within

hospitals (random intercepts). Intervention group (RFU vs. active COD vs. passive COD), baseline score, and time (3, 6, 12 months) are included as fixed effects, to determine the crude effect of the intervention. To correct for possible confounders, baseline variables will be added to the model as fixed effects.

The total number of surgical interventions at 1 year follow-up (11 years after surgery) will be presented by median and interquartile range. The number of complications will be compared between 3 groups, namely the RFU, active COD and passive COD, using GLMM, with a Poisson distribution. A random intercept for the centre will be included in the model to account for clustering within centres. GLMM will also be used to correct for and to investigate the effect of possible confounders..

The type of surgical interventions at 1 year follow-up (11 years after surgery) will be presented categorically by numbers and percentages. The type of surgical interventions will be compared between 3 groups using GLMM with logistic regression, adjusting for possible confounders and incorporating centre as a random intercept.

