4. STUDY POPULATION

4.1 Population (base)

Patients will be identified using the LROI register and the EPD. In 2015, 28,872 THA and 24,244 TKA were performed in the Netherlands [3]. The participating centres indicated that they performed between 400 and 800 THA and TKA per year. Taking into account a mortality rate of 16% 10 years after THA or TKA [18, 19], a revision rate of 6% 10 years after THA and TKA [3] and that 33% of the patients might not want to participate, the patient population will still be large enough to obtain our required sample size.

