8.1.2 Secondary study parameters/endpoints (if applicable)

- PROMIS physical function
- Number and type of surgical interventions (like DAIR, partial component exchange, revision surgery (full prosthesis replacement), irrigation and debridement (without component retention))
- Additional healthcare consumption related to THA or TKA FU (like clinical visit, telephone consultations, X-ray, CT scan, MRI scan, laboratory tests)
- Costs (based on electronic patient records and additional questionnaires, including all visits to healthcare professionals outside the hospital)
- Numeric Pain Rating Scale (NPRS)
- Numeric Satisfaction Rating Scale (NSRS)
- Health related quality of life (EQ-5D-5L)

For the passive COD group only available data from the EPD and LROI will be collected.

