8.2 Randomisation, blinding and treatment allocation

Participants are randomly assigned in a 1:1:1 ratio to one of the three groups: RFU, active COD or passive COD. In order to do so, randomisation takes place in two steps and will be done using Castor EDC.

First, patients will be randomly allocated in a 1:2 ratio to the active group and the passive COD (intervention) group, with use of dynamic block designed randomisation with blocks of 6, 9 and 12. From the passive COD group, 25 THA and 25 TKA patients will be randomly selected. Patients in the passive COD group are not informed about the study and are blinded. Only data from EPD and LROI register will be collected.

Second, patients who are not placed in the passive COD group will be informed about the study. After informed consent, they will be randomly allocated in a 1:1 ratio to group 1 (RFU, control) or group 2 (active COD, intervention) with use of dynamic block designed randomisation with blocks of 4 and 6 and stratification by center and procedure (TKA or THA). There patients are not blinded. Inclusion will stop once the groups are filled.

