10.1 Primary study parameter(s)

The total number of complications at 1 year follow-up (11 years after surgery) and process evaluation expressed by the health care consumption, like the number of clinical visits and X-rays, will be presented by median and interquartile range. For the primary aim, the number of complications will be compared between 2 groups, namely the RFU and active COD, using generalized linear mixed models (GLMM), with a Poisson distribution. A random intercept for centre will be included in the model to account for clustering of patients within centres and a main effect for group is added to determine treatment effect. We will also determine adjusted intervention effects, by accounting for relevant baseline characteristics such as age, gender, BMI, ASA-score, ethnicity, employment status, home-hospital distance and educational level.

The type of complications at 1 year follow-up (11 years after surgery) will be presented categorically by numbers and percentages. The type of complications will be compared between 2 groups (RFU vs. active COD) using GLMM with a logistic regression approach, including a main effect for group, a random intercept for centre and adjusting for baseline characteristics such as age, gender, BMI, ASA-score, ethnicity, employment status, home-hospital distance and educational level.

Process evaluation outcomes will also be expressed dichotomously (i.e. clinical visit: yes/no, X-ray: yes/no etc.) and analysed using logistic GLMM.

The primary outcomes are based on intention-to-treat analyses.

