11.2 Recruitment and consent

First, each participating center will select patients who had a THA or TKA 10 years ago using the LROI register and EPD. From this list, all patients will be selected who meet the inclusion and exclusion criteria. From the remaining list, patients will be randomized in a 1:2 ratio into a passive and active group. Patients in the active group will be approached for participation.

The initial contact regarding the study will be made by a physician working in the orthopaedic department of the hospital where the surgery was performed, by asking permission if he/she can be approached for the study. A researcher or research coordinator will contact the patient by phone, or at the outpatient department to assess their suitability for participation based on their medical history and the study's inclusion and exclusion criteria. The researcher will provide a brief overview of the study's purpose and procedures and offer the opportunity for patients to ask any initial questions about the study. If the patient expresses interest in the study, the patient information letter including the informed consent form will be sent by mail, along with a return envelope, and/or e-mail ensuring the patient has adequate time to review the study details. The patient will be contacted after at least 5 days by the research team. The researcher will discuss the patient information letter and the patient has the opportunity to ask further questions. Once the patient agrees to participate, they will sign the consent form and return it to the research team. The researcher will sign and return a copy of the fully signed consent form to the patient, ensuring that both the investigator and the patient have a complete signed informed consent.

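### The two contrasts with passive COD are not protected by randomisation, because that arm is allocated before consent while RFU and active COD hold only consenters; the primary comparison is unaffected

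*Protocol*

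**What the plan says.** Allocation has two steps. Protocol section 11.2 describes the first, applied to each centre's list of eligible patients: "From the remaining list, patients will be randomized in a 1:2 ratio into a passive and active group". Section 8.2 states that "Patients in the passive COD group are not informed about the study and are blinded", and that 25 THA and 25 TKA patients are then drawn at random from that group. For the second step, section 8.2 says that "patients who are not placed in the passive COD group will be informed about the study. After informed consent, they will be randomly allocated" 1:1 to RFU or active COD.

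Section 4.2 makes the questionnaire and consent criteria conditional on the patient completing questionnaires, so they do not filter passive COD. Section 4.1 allows that "33% of the patients might not want to participate".

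Section 2 sets a secondary objective on what informing patients about COD does to complications, visits, surgical interventions and costs. In section 10.2 the complication and visit models "will be repeated comparing the 3 groups, namely the RFU, active COD and passive COD", and surgical interventions are also compared across three groups. Nothing is said about consent. The linear mixed models for PROMIS, pain, satisfaction and EQ-5D-5L list passive COD as a level of the group factor and include a baseline score. Yet section 8.1.2 says: "For the passive COD group only available data from the EPD and LROI will be collected". Table 1 marks every questionnaire as not applying to that arm.

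**The concern.** A three-group model invites the reader to treat all pairwise contrasts alike, as comparisons of randomised groups. Here the first split is random, but the decliners on the active side then leave the study and appear in no analysis. Their counterparts on the passive side stay in. A difference between passive COD and either other arm can therefore reflect who agrees to take part, and not what being informed does.

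At stake is the objective on informing patients. Section 3 introduces the passive arm to avoid the trigger bias that contact and questionnaires might cause, so passive versus active COD is the contrast meant to show that effect. The selection falls on exactly this contrast. Covariate adjustment cannot be relied on to repair it, because willingness to take part is not among the listed covariates.

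**Working it through.** **1. The plan's own figure.** Section 4.4 gives 190 per group for RFU versus active COD (10% in both, limit of 10 points, 80%, two-sided 95% interval). Reading this as equivalence, with the 20% type II error split over the two sides:

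n = 2 × 0.10 × 0.90 × (1.960 + 1.282)² / 0.10² = 189.1, rounded up to 190.

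With 24% loss, 250 × 0.76 = 190. The figure reproduces. It concerns only the two consented arms, so nothing below changes it.

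**2. Composition of the arms.** Inputs: 33% refusal (section 4.1) and 250 per group per joint (section 4.4).

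- Would-be decliners in passive COD: 250 × 0.33 = 82.5, about 82 per joint.
- Decliners in RFU and active COD: none.
- Patients to approach for 500 consenters per joint: 500 / 0.67 = about 746.

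Drawing the passive patients at random from those allocated at step 1 does not alter this expected mix.

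**3. Size of the bias if informing patients has no effect.** Let p = 10% be the complication rate in consenters (the rate assumed in section 4.4), r = 33% the decliner share, and k the decliners' rate relative to consenters. The documents give no value for k, so 0.5 to 2 is an assumption.

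Passive COD rate = (1 - r) × p + r × p × k

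| k | Passive COD rate | Difference from consenters | Rate ratio |
|---|---|---|---|
| 0.5 | 0.067 + 0.0165 = 8.35% | -1.65 points | 0.84 |
| 1 | 0.067 + 0.033 = 10.0% | 0 | 1.00 |
| 1.5 | 0.067 + 0.0495 = 11.65% | +1.65 points | 1.17 |
| 2 | 0.067 + 0.066 = 13.3% | +3.3 points | 1.33 |

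Over the same range of k, the difference runs from -1.0 to +2.0 points at 20% refusal and from -2.5 to +5.0 points at 50%.

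**4. Effect on a nominal 5% test.** This uses a simple comparison of two proportions with 250 per arm and no loss to follow-up. It is an illustration and not the planned GLMM. For k = 2, SE = √(0.10 × 0.90/250 + 0.133 × 0.867/250) = 0.0287, so the bias is 0.033/0.0287 = 1.15 standard errors and the false-positive rate is about 21%. For k = 0.5 it is 9.8%, for k = 1.5 it is 9.1%, and for k = 1 it stays at 5%.

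**5. Questionnaire models.** No arithmetic is needed. Section 10.2 requires a baseline score and follow-up scores for passive COD; Table 1 and section 8.1.2 say that this arm has neither. The two cannot both be carried out.

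**The case against.** The strongest reply is that the comparison that matters is intact. RFU versus active COD is randomised after consent, is the primary analysis and the sizing basis, and stays randomised inside a three-group model. That stands. A reader might infer that the three-group analysis as a whole, or the trial, is not randomised. The documents do not support this: only the two contrasts with passive COD are affected.

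A reader might also infer that the adjusted models must fail because passive COD lacks ethnicity, employment status and education. Section 10.1 lists "age, gender, BMI, ASA-score, ethnicity, employment status, home-hospital distance and educational level", but only as examples, and section 8.3 says that baseline characteristics come from the EPD and LROI. The opt-out answer described in section 8.3 suggests self-report for ethnicity at least, but this is an inference, and extending it to employment and education is a further step. The model for the number of complications is also specified first with group and centre only, and that version would keep the passive arm in any case.

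A third tempting reading is that complications and visits are ascertained unequally. Section 8.3 takes healthcare use from the EPD and revisions from the LROI, and no listed questionnaire is said to capture complications. Unequal sources are firm only for costs, where a questionnaire covers what the EPD cannot supply, and for the patient-reported outcomes.

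Finally, the bias should not be read against the 10-point limit. That limit belongs to RFU versus active COD, which this bias cannot reach.

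**Conclusion.** The point holds for passive versus active COD and for passive COD versus RFU. Neither contrast is protected by randomisation, and section 10.2 presents them as if they were. The structure follows from sections 3, 4.2, 8.2 and 11.2 and needs no assumption.

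The size does need assumptions: 33% refusal is a planning figure, and the decliners' complication rate is not in the documents. Under an assumed 5% to 20% in decliners, the spurious difference is -1.65 to +3.3 points (rate ratio 0.84 to 1.33), with no bias if decliners and consenters have equal rates. The direction cannot be determined. Including passive COD in the questionnaire models is a plain contradiction. The primary comparison and the sample size are unaffected. The change should be made, but it concerns one secondary objective.

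**What to change.** Amend section 10.2 as follows.

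1. Label both contrasts with passive COD as non-randomised and supportive, and name active versus passive COD as the contrast for the informing objective.
2. Adjust these contrasts only for covariates obtained from the EPD or LROI in all three arms. Add complications and healthcare use from surgery to 10 years, which section 8.1.3 already collects. Leave out ethnicity, employment status and education if they prove to be self-reported only.
3. Compare costs involving passive COD only on items derived from the EPD or LROI.
4. Remove passive COD from the models for patient-reported outcomes.
5. Report a bounding analysis that puts the observed refusal fraction into the formula in the working, over a stated range for the decliners' rate. If EPD and LROI data on decliners may be used, add passive COD versus everyone allocated to the active group at step 1. That comparison keeps the first randomisation, but it mixes RFU and active COD and should be described so.

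The cost is a change of wording and one sensitivity table, with no change to sample size or conduct. The downside is a weaker claim for one secondary objective.

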3. STUDY DESIGN

During the grant application process, all relevant stakeholders were involved in setting up this study protocol during a co-creation process. The co-creation team consisted of representatives from patient associations, healthcare insurers, the knowledge institute of the federation of medical specialists, the national healthcare institute, methodological and statistical expertise, the Netherlands Orthopaedic Association (NOV), the ZE&GG program for appropriate healthcare, and the project team. ZE&GG organized meetings to discuss crucial points with the stakeholders, which resulted in a well-considered research protocol approved by all involved stakeholders. The NOV signed a declaration of support and commits to implementation of the results.

In this study a randomized controlled trial with 3 arms will be performed. Patients will be randomized 1:1:1 in the following groups:

[figure not shown]
1. RFU: routine follow-up at 10 years after THA or TKA (control)
2. Active COD: No RFU at 10 years. Patients will be informed about the study and complete questionnaires. Check-ups are scheduled only on demand by the patient or health care professional (HCP) (intervention)
3. Passive COD: No RFU at 10 years. Patients will not be informed about the study to avoid any trigger to contact a HCP and will not complete questionnaires (intervention)

Patients will be followed for 1 year after RFU or COD (11 years after surgery). Informing the patients about the study and letting them complete questionnaires might result in trigger bias to contact a HCP. Therefore, patients in the intervention group will be divided into two groups: 1) one group will be informed about the study and complete questionnaires (active COD), 2) the other group will not be contacted and informed about the study to avoid trigger bias (passive COD). Of the latest group, only data from the LROI and EPD will be used. The control group will receive RFU at 10 years after THA or TKA and will complete questionnaires. Both groups completing questionnaires (active COD and RFU group) will be actively asked to participate in the study and to complete questionnaires and therefore will be randomized after informed consent.

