8.3 Study procedures

This study will be conducted in 10 Dutch hospitals across the Netherlands. Patients will be recruited using the LROI register and EPD. After inclusion, baseline characteristics will be obtained from the EPD and LROI register. Information on patient background will be collected to explore potential differences in follow-up needs, including among patients with different ethnic backgrounds. Previous research shows that people with a migrant background visit specialists and hospitals less often than native Dutch patients with similar health and SES [21]. Acknowledging the sensitivity of this topic, a 'prefer not to say' option is provided.

Patients will be scheduled for a clinical visit or not depending on the randomization group. The clinical visit contains of a check by the orthopaedic surgeon or orthopaedic resident and an X-ray. Additionally, a physical examination can be performed in case of concerns.

Information about the clinical visit will be collected. The patient or the HCP can also schedule a clinical visit in case of concerns, pain or symptoms. Information about these visits will also be collected.

Patients randomized to the active COD or RFU group will be asked to complete the questionnaires online or on paper. Completion time will be around 10-25 minutes. Table 1 depicts the data collection and assessments at baseline and during follow-up appointments.

Study data will be collected onto an electronic case report form (eCRF) in Castor EDC. The primary outcome will be measured at 11 years after surgery, i.e. 1 year after RFU or COD at 10 years. EQ-5D-5L and costs will be measured at 10 years after surgery (baseline), and at 3, 6, and 12 months after baseline in the RFU and active COD group. The other outcomes will be measured only at 10 years (baseline) and 11 years after surgery (end point).

Table 1: Overview of data collection and assessments.

	Baseline (10 years after surgery) (+/- 30 days)	In case of check-up on demand (10-11 years after surgery)	3 months (+/- 30 days)	6 months (+/- 30 days)	12 months (11 years after surgery) (+/- 30 days)
Clinical visit	X*	X			
Physical examination [#]	X	X			
X-ray	X*	X [#]			
Healthcare consumption	X	X	X	X	X
Questionnaires:**					
PROMIS	X				X
EQ-5D-5L	X		X	X	X
NPRS	X				X
NSRS	X				X
Costs	X		X	X	X

* Only RFU group

[#] In case of concerns

** Not for passive COD group

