10.2.1 Cost-effectiveness

A trial-based economic evaluations will be performed at 11 years after surgery (i.e. 1 year after RFU or COD at 10 years), separated for THA and TKA. Both economic evaluations will be performed for the primary outcome (PROMIS physical function) and for QALYs, and in accordance with the intention-to-treat principle. We will consider two perspectives: 1) healthcare perspective and 2) societal perspective. QALYs will be estimated by multiplying the patients' utility values by the duration for which they experienced a certain health state [25, 26]. Utility values will be based on the EQ-5D-5L, which health states will be valued using the Dutch tariff. All other kinds of resource utilization will be assessed using cost questionnaires administered at baseline, and 3, 6 and 12 months, and valued according to the "Dutch manual of costing" [27].

Missing data will be imputed using multivariate imputation by chained equations [28]. From the societal perspective, costs will include healthcare costs, absenteeism, presenteeism, unpaid productivity, and informal care costs. From the healthcare perspective, only costs accruing to the formal Dutch healthcare sector will be included. Costs will be assessed using cost questionnaires, and valued in accordance with the Dutch manual of costing. Cost and effect differences will be estimated using linear mixed models. It is very important to use mixed-model analyses, and hence to account for the possible clustering of cost and effect data (e.g., at the hospital level), as most economic evaluations fail to do so, whereas ignoring the possible clustering of data might lead to inaccurate levels of uncertainty and inaccurate point estimates. Incremental cost effectiveness ratios (ICERs) will be calculated by dividing

the difference in costs by that in effects. Bootstrapping techniques will be used to estimate the uncertainty surrounding the cost-effectiveness estimates (please note that non-parametric bootstrapping will be nested within the multiple imputation procedure). Uncertainty will be shown in cost-effectiveness planes and cost-effectiveness acceptability curves [29,30]. The latter indicate the probability of COD being cost-effective compared with RFU at different values of willingness to pay. Multiple sensitivity analyses will be performed to test the robustness of the cost-effectiveness results derived from the main analysis (e.g. complete-case analysis) [26].

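### The section 10.2 model for patient-reported outcomes includes an arm and, for three of four instruments, time points that the protocol does not measure, and it adjusts for a baseline score not fixed before allocation or the RFU visit

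*Protocol*

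**What the plan says.** **The model.** Protocol section 10.2 covers "Secondary patient-reported outcomes, namely PROMIS physical function, NPRS, NSRS and EQ-5D-5L" with one specification. It continues: "These parameters will be analysed using linear mixed models, with repeated measures clustered within participants and participants within" hospitals, with random intercepts. The fixed part is: "Intervention group (RFU vs. active COD vs. passive COD), baseline score, and time (3, 6, 12 months) are included as fixed effects".

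**Who supplies the data.** Section 3 says of the passive COD arm: "Patients will not be informed about the study to avoid any trigger to contact a HCP and will not complete questionnaires (intervention". Section 8.1.2 limits that arm to patient-record and registry data. In section 8.3 the Table 1 footnote to the questionnaires reads "Not for passive COD group".

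**When the data are collected.** Section 8.3 gives EQ-5D-5L and costs at baseline, 3, 6 and 12 months, in RFU and active COD only. For the rest: "The other outcomes will be measured only at 10 years (baseline) and 11 years after surgery (end point").

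**Where baseline sits.** Section 8.2 randomises to RFU or active COD after consent and says these patients are not blinded; it places no questionnaire before that step. Section 8.3 says: "Patients randomized to the active COD or RFU group will be asked to complete the questionnaires online or on paper". Table 1 has a single baseline column with a 30-day window either side. It holds the baseline questionnaires together with the RFU visit and X-ray.

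**Label.** Section 10.2.1 says: "Both economic evaluations will be performed for the primary outcome (PROMIS physical function) and for QALYs". The Summary and section 8.1.2 list PROMIS physical function as secondary. Section 8.1.1 names complications and healthcare consumption as the main endpoints.

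**The concern.** The analysis section and the data schedule describe different trials for the patient-reported outcomes. One arm in the model has neither outcome nor baseline score, and for three of the four instruments two of the three time points do not exist. An analyst would have to change the model after the fact, and the protocol does not say how.

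The baseline covariate is a separate matter. Adjusting for a baseline score is sound when the score is fixed before allocation. Here patients may know their arm, and RFU patients may have had their visit and X-ray, before they answer. NSRS asks about satisfaction with the treatment result and EQ-5D-5L has an anxiety item, so a check-up could plausibly move either. A score that already carries part of the arm effect takes that part out of the estimate when it is used as a covariate, and this cannot be repaired once the data are in.

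PROMIS physical function and QALYs from EQ-5D-5L are also the effect measures of the economic evaluation, and cost-effectiveness is part of the primary objective in section 2. The measurements therefore matter beyond the secondary tables.

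**Working it through.** **1. The protocol's own figure.** The only calculated size is in section 4.4, for complications: 10% in both groups, a 10-point margin, a two-sided 95% interval and 80% power. For equivalence, n = 2p(1 - p)(z0.975 + z0.90)^2 / margin^2 = 2 x 0.10 x 0.90 x (1.960 + 1.282)^2 / 0.10^2 = 189.1, so 190 per group, as stated. Allowing 24% loss gives 190 / 0.76 = 250. This calculation uses no patient-reported outcome, so the point raised here does not affect it.

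**2. Which terms can be estimated.** The fixed part has six terms: intercept, two arm terms, baseline score and two time terms. With 250 randomised per group and complete data:

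| Case | Rows | Estimable terms |
|---|---|---|
| As written: 3 arms x 3 times | 3 x 3 x 250 = 2,250 | 6 of 6 |
| EQ-5D-5L as scheduled: 2 arms x 3 times | 2 x 3 x 250 = 1,500 | 5 of 6 |
| PROMIS, NPRS, NSRS as scheduled: 2 arms x 1 time | 2 x 1 x 250 = 500 | 3 of 6 |

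These counts are the ranks of the fixed-effects matrix on the rows that Table 1 allows. EQ-5D-5L loses only the passive COD term. The other three lose that term and both time terms. They also have one outcome value per participant, because baseline enters as a covariate. The participant intercept then cannot be separated from the residual.

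**3. Effect of a baseline score taken too late.** The protocol gives no figure for either input, so both are assumptions: r is the correlation between the baseline and 12-month scores, and f is the fraction of the 12-month arm effect (delta) already in the baseline score.

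- Adjusted estimate = delta - beta x (baseline difference between arms).
- The baseline difference is f x delta, and beta is about r when the two scores have equal spread.
- Expected estimate = delta x (1 - r x f).

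A simulation with 190 per arm, SD 10, a true effect of 3 points and 1,000 replicates agrees with the formula:

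| r | f | Formula | Simulated share kept |
|---|---|---|---|
| 0.5 | 0 | 1.00 | 1.00 |
| 0.5 | 0.5 | 0.75 | 0.76 |
| 0.5 | 1 | 0.50 | 0.51 |
| 0.7 | 0 | 1.00 | 0.99 |
| 0.7 | 0.5 | 0.65 | 0.65 |
| 0.7 | 1 | 0.30 | 0.31 |

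The sign of f matters. If the visit moves the early score in the opposite direction to the 12-month effect, f is negative and the estimate is inflated: with r = 0.7 and f = -0.5 the factor is 1 + 0.35 = 1.35.

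**4. The label.** The Summary, section 8.1 and section 10.1 agree on complications and healthcare consumption as primary. Only the parenthesis in section 10.2.1 differs.

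**The case against.** **The model will run.** A reader might infer that the analysis cannot be carried out at all. That goes too far: software would drop the empty arm and time levels and return RFU versus active COD, which is the sensible comparison. Section 2 points the same way, since its objective on informing patients names no patient-reported outcome. The three-group wording may have been carried over from the neighbouring count models. This limits the harm, but the stated contrasts still do not exist and the text still needs correcting.

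**Imputation.** A reader might infer that the passive arm's scores would be imputed wholesale. Section 10 provides for multiple imputation only where it is needed and feasible, and nothing plans it for an arm that is never asked. With no observed score in that arm it would have nothing to draw on.

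**Baseline order.** The sentence on who completes questionnaires can be read as identifying the respondents, not setting a sequence, and no section puts the questionnaire after the visit. That is fair: this is an order left open, not a documented error. A reader might infer that most of the effect will be adjusted away. That needs f near 1 and a high r, neither of which is in the protocol, and the direction depends on the sign of f.

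**EQ-5D-5L over time.** A reader might call the absence of a group-by-time term an error, because the objective refers to one year. A main effect averaged over follow-up is a legitimate choice, so this is a preference and no part of the point.

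**The label.** A reader might infer that the trial has two competing sets of primary outcomes. The sections that define and analyse the primary endpoints agree with each other, so one parenthesis in the economic section does not amount to that.

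**Conclusion.** The contradiction stands on the text alone. The passive COD contrast is not estimable for any of the four instruments, and the time terms and participant intercept are not estimable for PROMIS, NPRS and NSRS. EQ-5D-5L fails only on the passive arm. The label in section 10.2.1 is wrong. None of this depends on an assumption, and none of it is detail that an unseen SAP would be expected to supply, because the protocol's own sections disagree.

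The baseline point is a risk that the text permits. Under assumed values of r from 0.5 to 0.7, about 65% to 76% of the effect would remain at f = 0.5 and 31% to 51% at f = 1. There is no loss if the score is taken before the patient knows the arm and before the visit.

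The primary complication analysis and the 190 and 250 per group are unaffected. The point should be fixed, but it does not put the main result in doubt.

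**What to change.** - In section 10.2, restrict the patient-reported outcome models to RFU versus active COD.
- Analyse PROMIS, NPRS and NSRS at 12 months, adjusted for baseline score, with a centre intercept and no time term or participant intercept. Keep the 3-, 6- and 12-month time terms for EQ-5D-5L only.
- In sections 8.2 and 8.3, state that the baseline questionnaires are completed after consent and before the RFU or active COD allocation is released, which also places them before any RFU visit.
- In section 10.2.1, call PROMIS physical function a secondary outcome.

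The first, second and fourth changes are wording only. The third reorders two steps and needs no new data. Its price is an extra step before randomisation, and some patients who do not complete the baseline questionnaires may not be randomised. How many is not known from the protocol; section 4.1 already allows for 33% declining to take part, so recruitment should be watched.
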